6.11.2.4 Analyses of Other Secondary Efficacy Variables

Comparisons between treatment arms for all other secondary endpoints such as Pruritus Evaluation (Likert scale and Itchy QoL) will be conducted with no adjustment for multiple comparisons used for those statistical tests.

PFS and ORR as assessed by the IR will be analyzed using the same method described above for PFS and ORR as assessed by the Investigator.

Frequency tables will be used to display the best overall response as assessed by the Investigator and by the IR during the randomized treatment period for all subjects by treatment arm. The concordance between the investigators assessment and the IR assessment of best overall responses will be presented.

For subjects who achieved a confirmed CR or PR during the randomized treatment period, the time to response will be summarized descriptively. The duration of response will be analyzed using survival analysis methods. The Kaplan-Meier estimate of the median duration of response and the associated 95% confidence intervals will be estimated and presented separately for each treatment arm. Because the DOR is a conditional estimate (conditional on having a confirmed response), comparison between KW-0761 and vorinostat would not be based on randomized groups and therefore will not be made.

The same repeated measures ANCOVA model described above for the analysis of change in Skindex-29 score from baseline to end of cycles 1, 3, and 5 will be performed for the changes in Skindex-29 score, FACT-G total score and EQ-5D-3L index score at other time points up to end of cycle 11. Due to the relatively small sample size of subjects after cycle 11, QoL data beyond cycle 11 will only be summarized descriptively. In addition, for EQ-5D-3L descriptive system, frequency tables will be used to display the number and percentage of subjects with reported problems for each level and for each dimension at each scheduled timepoint.

Other quality of life measurements including changes in Pruritus Evaluation (Itchy QoL score) and EQ-5D-3L VAS score from baseline at each scheduled timepoint up to the cycle 11 assessment will also be analyzed using the same method. The assumptions of normality and homogeneity of variance of the ANCOVA analysis will be examined prior to fitting the models. When significant departure from the assumption is observed, the Wilcoxon rank sum test will be applied.

For the Pruritus Evaluation Likert Scale data, the changes in the Likert Scale score from baseline at different timepoints up to the cycle 11 assessments during the randomized treatment period will be analyzed using Wilcoxon rank sum test. The treatment difference in the median change of the Likert Scale score from baseline will be estimated using the Hodges-Lehmann estimate and a two-sided 95% confidence interval for the treatment difference will be obtained using the method of Moses.

All quality of life measurements and changes from baseline will be summarized descriptively at each scheduled time point.

For subjects who cross over from the vorinostat arm to the KW-0761 arm, ORR during the crossover portion of the trial will be estimated in a similar fashion as described above for ORR of the randomized therapy. In addition, the quality of life assessments during the crossover portion will be measured at the end of the first cycle after the first day of dosing for KW-0761. Baseline measurements for the crossover portion are considered to be those taken at the last assessment point of the previous cycle. The quality of life measurements as well as the changes from baseline during the crossover portion of the trial will be summarized descriptively. All summaries for the crossover portion will be purely descriptive. No statistical comparisons will be made for data collected during the crossover portion.

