The duration of response (DOR), which will be estimated using survival analysis methods, is measured from the time measurement criteria are met for CR/PR (whichever is first recorded) until the first date that PD or death is objectively documented (taking as a reference for PD that smallest measurement recorded since the treatment started). Subjects who do not relapse will be censored at the day of their last tumor assessment. The DOR will be estimated separately for each treatment arm. Because the DOR is a conditional estimate (conditional on having a response), comparison between KW-0761 and vorinostat would not be based on randomized groups and therefore will not be made.

The Pruritus Evaluation (Likert scale & Itchy QoL) and Skindex-29, FACT-G and EQ-5D-3L assessments will be summarized at baseline and at the timepoints specified in the study procedures tables for each arm. The improvement (change from baseline) for each of these measures will also be summarized and analyzed using repeated measures ANCOVA utilizing time points through the 6-month assessment.

For those subjects who crossover from the vorinostat arm to the KW-0761 arm, these assessments within the second arm of the study will be measured at the end of the first cycle after the first day of dosing for KW-0761. Baseline measurements for crossover subjects are those documented closest to and before the first KW-0761 infusion. No statistical comparisons will be made for information gathered in the crossover from the vorinostat arm to the KW-0761 arm. All summaries for this arm will be purely descriptive.

Progression-free survival is the primary endpoint in this study. There are four key secondary endpoints in this study that require a comparison between treatment arms: ORR, Skindex-29, FACT-G, and EQ-5D-3L. Comparisons of these four secondary endpoints between the 2 treatment arms will be conducted using p-values that are adjusted to control the overall study-wise Type 1 error rate to be less than 0.05. Since these tests are not independent, the four secondary tests will be conducted using the Sidak adjusted p-value method defined as **Adjusted p-value = $1-(1-p)^4$** where **p** is the original p-value of the individual test

These adjusted p-values will then be compared to .05 for each test.

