Comparisons between treatment arms for all other secondary endpoints such as Likert scale, and Itchy QoL will be conducted with no adjustment for multiple comparisons used for those statistical tests. Exploratory subset analyses for PFS and any of the secondary endpoints by region, study site, compartment involvement, CCR4 expression status, disease subtypes, and medical history may be conducted. Details of such subset analyses will be provided in the Statistical Analysis Plan. Although overall survival (OS) is not a secondary endpoint, each subject will be followed in this study for a minimum of 2 years to generate information on OS. Using this follow-up information, a comparison between treatment arms for OS will also be conducted and considered exploratory. Statistical analyses on OS using follow-up data may take place after database lock for the study and will be reported as supplemental to the Clinical Study Report.

Randomization will be stratified within the 2 disease types, SS and MF and 2 disease stages IB or II and III or IV. The efficacy analyses described in this section will be conducted as stratified tests but may also be conducted as a subset analysis within each of these disease-type groups and disease stages. Comparison of endpoints between these 2 groups and

stages will be conducted for each treatment assuming adequate sample sizes in the respective groups.

Exploratory analyses based on other subject groupings and with other parameters may also be conducted.

Since the primary endpoint is PFS, the reference median PFS for vorinostat is assumed to be 169 days. The median PFS for KW-0761 therapy is targeted for 254 days, a 50% improvement over this reference median. For a 24-month accrual and 12 month follow-up on the last subject dosed, [Table 10.3-1](#) gives the power and the number of PFS events required to show superior PFS for KW-0761 therapy over vorinostat at the one-sided 0.025 significance level. The ITT set is used for this primary analysis. The same analysis conducted using the Efficacy Evaluable set is considered secondary.

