8.2.5 SAS[®] Procedures

This section provides sample SAS[®] code to illustrate statistical tests specified in the statistical methods section. All computer output from SAS[®] statistical procedures serving as a basis for extracted results (e.g., LIFETEST) will be retained for quality control procedures and will be included in CSR appendices.

- 1) Stratified Log Rank test for PFS between treatment:

```
proc lifetest method=KM;
    time PFS*censor(1);
    strata type stage region/group=trt;
run;
```
- 2) Hazard ratio from Cox proportional hazard model for PFS:

```
proc phreg;
    model PFS*censor(1)=trt type stage region/risklimits ties=efron;
run;
```
- 3) CMH test for ORR between treatment:

```
proc freq;
    tables type*stage*region*trt*resp/cmh;
run;
```
- 4) Exact 95% confidence interval on ORR and exact 95% unconditional confidence interval for the risk difference:

```
proc freq;
    tables trt*resp;
    exact riskdiff;
run;
```
- 5) ANCOVA for change in QoL score between treatment:

```
proc mixed;
    class trt type stage region timept usubjid;
    model QoL_chng = trt type stage region base_QoL timept
        trt*timept/solution;
    repeated timept / subject=usubjid type=un;
    lsmeans trt/pdiff cl;
run;
```
- 6) Wilcoxon Rank Sum test for change in Likert Scale score between treatment:

```
proc npar1way wilcoxon hl;
    class trt;
    var QoL_chng;
run;
```

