Summary of Pruritus Evaluation Itchy Quality of Life Score and Change from Baseline by Visit During Crossover Portion
Intent-to-Treat Set
Subjects Who Are Randomized to Vorinostat and Crossed Over to KW-0761

<<Programming Note:

(1) Only the overall score will be presented for Itchy Quality of Life.

(2) For tables 14.2.7.1, 14.2.7.3, and 14.2.7.5, all scheduled timepoints according to the study procedures will be presented.>>

The following table will have a similar layout as Table 14.2.3.1:

Table 14.2.8.1
Summary of Pruritus Evaluation Likert Scale Score and Change from Baseline by Visit During Randomized Treatment Period
Intent-to-Treat Set

<<Programming Note: For Table 14.2.8.1, add a row in each time point to display interquartile range after median.>>

Table 14.2.8.2
 Analysis of Change in Pruritus Evaluation Likert Scale Score from Baseline
 During Randomized Treatment Period
 Intent-to-Treat Set

Time Point Treatment	N*	-----Change from Baseline-----				--Treatment Difference (KW-0761 vs. Vorinostat)--		
		--Baseline-- Median (IQR)	--Endpoint-- Median (IQR)	Median (IQR)	95% CI	Median (IQR)	95% CI	P-value
End of Cycle 1								
Vorinostat	xxx	xx.x (xx.xx)	xx.x (xx.xx)	xx.x (xx.xx)	(xx.x, xx.x)	xx.x (xx.xx)	(xx.x, xx.x)	x.xxxx
KW-0761	xxx	xx.x (xx.xx)	xx.x (xx.xx)	xx.x (xx.xx)	(xx.x, xx.x)			
End of Cycle 3								
Vorinostat	xxx	xx.x (xx.xx)	xx.x (xx.xx)	xx.x (xx.xx)	(xx.x, xx.x)	xx.x (xx.xx)	(xx.x, xx.x)	x.xxxx
KW-0761	xxx	xx.x (xx.xx)	xx.x (xx.xx)	xx.x (xx.xx)	(xx.x, xx.x)			
End of Cycle 5								
Vorinostat	xxx	xx.x (xx.xx)	xx.x (xx.xx)	xx.x (xx.xx)	(xx.x, xx.x)	xx.x (xx.xx)	(xx.x, xx.x)	x.xxxx
KW-0761	xxx	xx.x (xx.xx)	xx.x (xx.xx)	xx.x (xx.xx)	(xx.x, xx.x)			

Etc.

* N is the number of subjects with values at baseline and post-baseline.

Note: Treatment difference (KW-0761 - Vorinostat) and its 95% CI are estimated using Hodges-Lehmann estimator and Moses method.

P-values are obtained from Wilcoxon Rank Sum test. Time points beyond Cycle 11 are not included due to the small number of subjects on study after cycle 11.

The following tables will have similar layout as Table 14.2.8.1 and Table 14.2.8.2:

Table 14.2.8.3
Summary of Pruritus Evaluation Likert Scale Score and Change from Baseline by Visit During Randomized Treatment Period
Intent-to-Treat Set

Table 14.2.8.4
Analysis of Change in Pruritus Evaluation Likert Scale Score from Baseline
During Randomized Treatment Period
Intent-to-Treat Set

Table 14.2.8.5

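### The pruritus Likert score gets separate unstratified Wilcoxon tests of change at each visit instead of the protocol's repeated-measures ANCOVA: valid, but less precise, and not flagged as a departure

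*SAP*

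**What the plan says.** **Protocol.** Comparing pruritus improvement by Likert scale and Itchy QoL is a secondary objective (Protocol 2.2). Section 10.3 names the Likert scale among the measures concerned: "The Pruritus Evaluation (Likert scale & Itchy QoL) and Skindex-29, FACT-G and EQ-5D-3L assessments will be summarized at baseline". The change from baseline in each of them is to be "analyzed using repeated measures ANCOVA utilizing time points through the 6-month assessment". The same section adds: "The efficacy analyses described in this section will be conducted as stratified tests". The strata are disease type (MF or SS) and disease stage (IB/II or III/IV).

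**SAP.** In 6.11.2.4, changes in the Likert score at the different timepoints up to Cycle 11 "during the randomized treatment period will be analyzed using Wilcoxon rank sum test". For the effect size, "The treatment difference in the median change of the Likert Scale score from baseline will be estimated using the Hodges-Lehmann estimate", with a confidence interval by the method of Moses. The code in 8.2.5, item 6, is "proc npar1way wilcoxon hl", with treatment as the class and change as the variable and nothing else. The shell of Table 14.2.8.2 has one p-value per visit and no overall row; its footnote says "P-values are obtained from Wilcoxon Rank Sum test".

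**The other scores.** Skindex-29, FACT-G and the EQ-5D-3L index have a mixed model with time, region, disease type, disease stage, treatment, time-by-treatment and baseline score (SAP 6.11.2.3). Itchy QoL, the other half of the pruritus objective, uses the same method (6.11.2.4). For these scores the Wilcoxon test is only a fallback if model assumptions fail.

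**Departures.** SAP section 1 states that the SAP supersedes the protocol's statistical text and that substantial differences will be identified in the SAP. Neither 6.11.2.4 nor the Summary of Revisions identifies this one. The summary does record added quality-of-life testing beyond 6 months, but not the Likert method.

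**The concern.** Two measures serve one secondary objective, and the SAP analyses them differently without giving a reason. For the Likert score it leaves out three things the trial already has:

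- the baseline score as a covariate, which predicts the follow-up score;
- disease type and stage, on which randomization was stratified;
- the joint use of visits. If the shell keeps to odd cycles up to 11, it yields six unadjusted p-values (Cycles 1, 3, 5, 7, 9, 11) with no lead visit and no summary contrast.

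At stake is how clearly the trial can answer the itch question. A real difference is more likely to be missed or estimated loosely, and a reader faced with several visit-wise p-values has no pre-specified one to look at first.

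**Working it through.** **1. The plan's own figure.** The documents give no power, SD or effect for the Likert score. The only sizing figure is 255 PFS events for 90% power at one-sided 0.025. It reproduces: with hazard ratio 169/254 = 0.665, 4(1.960 + 1.282)² / (ln 0.665)² gives 254 events, and power at 255 events is 90.2%. It says nothing about the Likert score. The 317 enrolled subjects do give an upper bound of about 159 per arm (317/2).

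**2. Precision in normal theory, one visit.** Let r be the correlation between baseline and follow-up score, with equal SDs. It is not in the documents, so 0.3 to 0.8 is assumed.

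- Variance of raw change: 2(1 − r)·SD²
- Variance after baseline adjustment: (1 − r²)·SD²
- Ratio, adjusted to change: (1 − r²) / [2(1 − r)] = (1 + r)/2

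The Wilcoxon test has a further efficiency factor of 3/π = 0.955 under normality. With relative efficiency E, its power when ANCOVA has power P is Φ(√E·(1.96 + z_P) − 1.96).

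| r | (1+r)/2 | E = (1+r)/2 × 3/π | Wilcoxon power if ANCOVA has 80% | if ANCOVA has 90% |
|---|---|---|---|---|
| 0.3 | 0.65 | 0.62 | 60% | 72% |
| 0.5 | 0.75 | 0.72 | 66% | 78% |
| 0.7 | 0.85 | 0.81 | 71% | 83% |
| 0.8 | 0.90 | 0.86 | 74% | 85% |

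**3. Simulation on an integer 0–10 score.** Assumed: 159 per arm, SD 2.7, a disease-type shift of 0.5 SD, complete data. Effects of 0.87, 0.79, 0.65 and 0.54 points were chosen to put ANCOVA power in the 80s. Both adjusted methods include disease type and stage.

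| r | Wilcoxon on change | ANCOVA | Rank ANCOVA |
|---|---|---|---|
| 0.3 | 64% | 82% | 80% |
| 0.5 | 68% | 83% | 81% |
| 0.7 | 74% | 82% | 78% |
| 0.8 | 76% | 83% | 81% |

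With no treatment effect (100 per arm, r = 0.5), rejection rates were 5.0% for Wilcoxon, 4.2% for ANCOVA and 4.4% for rank ANCOVA.

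A separate simulation fixed the effect at 0.8 points (120 per arm, SD 2.5, three strata) and compared Wilcoxon with a within-stratum rank ANCOVA. Power was 53% versus 69% at r = 0.3, 66% versus 76% at 0.5, and 86% versus 89% at 0.7.

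**4. Less convenient data.** At 120 per arm, Wilcoxon versus ANCOVA power was:

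| Underlying r | Floor effect | Proportional effect | Heavy-tailed (t, 3 df) errors |
|---|---|---|---|
| 0.3 | 59% vs 81% | 46% vs 69% | 54% vs 77% |
| 0.5 | 73% vs 87% | 58% vs 75% | 72% vs 83% |
| 0.7 | 90% vs 96% | 79% vs 90% | 91% vs 92% |
| 0.8 | 97% vs 99% | 91% vs 96% | 98% vs 97% |

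**5. Baseline imbalance.** If the arms differ at baseline by D, the change-score contrast carries (r − 1)·D: 70%, 50% or 30% of D at r = 0.3, 0.5 or 0.7, in the reverse direction. It averages to zero under randomization.

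**The case against.** The case for leaving the plan alone has real weight.

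- **Low consequence.** The Likert score is not one of the four Sidak-controlled key secondary endpoints. It is tested without multiplicity adjustment, and Itchy QoL covers the same objective with the adjusted model. This stands and limits the importance of the point.
- **A rank method suits the scale.** The score is a single bounded 0–10 item, whereas the questionnaire scores given the model average or sum several items. This also stands, but it supports ranks, not the omission of baseline and strata. The rank ANCOVA in step 3 kept 78% to 81% power.
- **It is pre-specified.** Text, code and shell agree, and the SAP was finalized before database lock. True, but what section 1 also asks for, identification of the difference, is missing.
- **The protocol's model is thinly described.** Section 10.3 names no covariates and stops at 6 months, and region is a SAP addition. The full covariate list is therefore the SAP's own model for the other scores.

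A reader might also infer more than the documents support:

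- *The comparison is invalid.* It is not; the type I error is about 5%.
- *Baseline is ignored altogether.* Change still subtracts it; what is absent is baseline as a covariate.
- *Chance baseline imbalance passes straight into the result.* Only the fraction in step 5 does.
- *The trial loses a known amount of power.* The documents contain no r, SD or effect from which to derive one.

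**Conclusion.** The point holds as a loss of precision and an unflagged departure on an other-secondary measure. It does not touch the primary analysis or any of the Sidak-controlled endpoints.

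The firmest result on size is the normal-theory ratio: baseline adjustment brings the single-visit variance to 0.65–0.85 of the change-score variance for r of 0.3–0.7. This rests on equal SDs and the assumed r. The power figures are illustrations. Across the settings tried, the gain ranged from about 20 points at low r to a few points or none at high r, and with heavy-tailed errors at r of 0.7–0.8 the methods tied. The simulations assume complete data. Fewer patients will be assessed at late visits, so the group sizes used are optimistic there.

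**What to change.** 1. Make the main Likert analysis the repeated-measures model of SAP 6.11.2.3: baseline score, disease type, disease stage, region, visit, treatment and treatment-by-visit. Report one overall contrast over the ends of Cycles 1, 3 and 5, plus visit contrasts.
2. State that the switch to an unadjusted Wilcoxon test in 6.11.2.3 and 6.11.2.4 does not apply to this score. On a bounded integer item, an assumption check could otherwise lead back to the same test through a data-dependent choice.
3. Pre-specify, as the robust sensitivity analysis, a rank ANCOVA stratified by disease type and stage with baseline rank as covariate. If the sponsor prefers a rank method for a single 0–10 item, this can be the main test.
4. Keep the Hodges-Lehmann estimate as descriptive.
5. State in the SAP any remaining difference from Protocol 10.3 and the reason for it.

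The cost is SAP wording, one code block in 8.2.5, a revised Table 14.2.8.2 shell (and its Efficacy Evaluable counterpart) and a little more analysis work. No new data are needed. The change should be made before database lock.
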